9. INTERRUPTION OF TREATMENT

This section deals with a patient's premature withdrawal from the study before completing all scheduled visits. An individual subject may be withdrawn at the discretion of the responsible investigator and the study team for the reasons listed hereby. In the event one or more subjects are withdrawn, additional subjects may be enrolled to ensure an adequate number of subjects complete the cohort.

Reasons that a patient must discontinue participation in a clinical study are considered to constitute one of the following:

1. unsatisfactory therapeutic effect (quarterly increase in ferritin levels of at least 1500 ng/ml as detected by two determinations performed at no more than two weeks interval, or if cardiac MRI T2* decreases under 10ms)
2. subject's condition no longer requires study treatment
3. DFX treatment at 10 mg/kg/day (for safety reasons) for more than 4 weeks
4. DFP or DFX administration suspended (for safety reasons) for more than 4 weeks
5. adverse event(s) requiring change of chelation therapy, including moderate or severe Neutropenia
6. significant protocol violation
7. subject/legal guardian withdrew consent/assent
8. lost to follow-up
9. administrative problems
10. death

In the absence of a medical contraindication or significant protocol violation, the investigator may make an effort to keep the subject in the study. Should a subject withdraw or be withdrawn by the legal guardian, he/she has to complete a full set of the 'end-of-study phase assessments', i.e. a full V16 evaluation. Relevant records will have to be done on the corresponding CRF pages.

This requirement does not refer to patients who passed the screening and washout period and were found not to be eligible for treatment.

Patients prematurely withdrawn from the treatment will be considered treatment failures.

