Serum ferritin will be tested in terms of quantitative variable as part of the composite endpoint measurable in the entire experimental population. The purpose of this analysis is to clarify the interpretation of the primary composite endpoint and hence no adjustment for multiplicity will be considered. The population for this analysis is the PP2. ITT analysis will be used to corroborate the findings.

Non inferiority of DFP to DFX will be tested considering a non inferiority margin of 400 ng/mL.

Non-inferiority will be assessed based on the two sided 95% confidence interval $[\delta_L, \delta_U]$ of the difference $\delta = m_1 - m_2$, being m_1 and m_2 the mean difference between baseline and end of treatment assessments of DFP and DFX, respectively, and n_1 and n_2 the numbers of patients randomised to DFP and DFX arms. Non-inferiority will be claimed if δ_L is greater than -400 ng/ml.

The two sided 95% confidence interval for δ will be estimated as follows:

$$(m_1 - m_2) \pm Z_{1-\alpha/2} \sigma \sqrt{\frac{1}{n_1} + \frac{1}{n_2}}$$

where Z_γ is the γ^{th} percentile of the standardised normal distribution and σ^2 is the pooled variance.

Serum ferritin trends over the 1 year period of treatment will be also investigated. A repeated measures analysis of variance model with treatment-group as main effect will be fitted. The H_0 of equal between group regression slopes will be tested by evaluating whether the interaction between the categorical factor (treatment group) and the repeated measure (monthly measures of serum ferritins) equals zero, i.e. no interaction. The rejection of the null hypothesis on the interaction term (treatment group*monthly ferritin measure) will be supportive of different trends between DFP and DFX arms. The ITT population will be used for this analysis. Handling of missing data for this analysis is described in Section 11.4.

Descriptive statistics for trends in subgroups of patients according to age classes will be also provided.

Efficacy measured through cardiac T2* MRI

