11.13 Handling of missing data

A negligible amount of missing data is expected in this study because the patient population under study (patients affected by haemoglobinopathies requiring chronic transfusion and chelation therapy), and their parents, are accustomed to routine close monitoring in clinical visits, are used to frequent lab tests and comply with uncomfortable examinations (MRI), and are generally willing to participate in trials that may lead to increasing the availability of treatments. Moreover, the estimated treatment effect is not expected to be importantly biased in favour of the experimental treatment due both to the choice of the comparator and of the primary endpoint.

DFX is an oral chelator as DFP, and its compliance is expected to be comparable to that of DFP, or even better taking into account the once a day administration.

The completeness of the data that will allow the estimate of the primary endpoint (percentage of successfully chelated patients) is expected to be high due to the type of patients and condition.

Finally, patients who prematurely discontinue the trial for any reason will be considered treatment failures.

Assuming the worst scenario for incomplete data in order to provide conservative estimates for the trial results, the imputation of missing data will only apply to missing data because of a missing visit. This will affect the trend analysis for the secondary evaluation on serum ferritin levels. In this case, Linear Mixed Models (LMM) will be used as imputation method for missing data.

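### The ferritin trend test should be a mixed model fitted to all observed values; as written, discontinued patients can drop out of an analysis labelled ITT, mainly at a cost in power

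*Combined protocol and SAP*

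**What the plan says.** Section 11.6 (secondary efficacy, serum ferritin) defines the trend analysis: "A repeated measures analysis of variance model with treatment-group as main effect will be fitted". The hypothesis is that the arms have the same trend: "The H_0 of equal between group regression slopes will be tested", through the treatment-by-time interaction. The population is stated: "The ITT population will be used for this analysis". For missing values the reader is sent elsewhere: "Handling of missing data for this analysis is described in Section 11.4". Section 11.4 covers demographic characteristics and contains no missing-data rule; the rule is in Section 11.13.

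Section 11.13 makes the mixed model the imputation tool ("Linear Mixed Models (LMM) will be used as imputation method for missing data") and limits its scope: "the imputation of missing data will only apply to missing data because of a missing visit". For discontinuation it says that "patients who prematurely discontinue the trial for any reason will be considered treatment failures". It expects missing data to be negligible, whereas Section 11.12 allows for about 20% dropout.

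Section 9 lists ten reasons for leaving the study. The first includes "unsatisfactory therapeutic effect (quarterly increase in ferritin levels of at least 1500 ng/ml", confirmed by a second determination. Sections 7.2.5 and 7.3.12 call for a central ferritin at withdrawal. Sections 4.4.1 and 7.3.12 base formal analyses on central values, which are quarterly, but Section 11.6 describes the repeated measure as monthly.

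**The concern.** The two sections do not fit together. A classical repeated-measures ANOVA uses only patients with a value at every time point. Imputation fills gaps for patients who miss a visit and return. For those who leave, the only rule is the failure label, which serves a binary endpoint but gives no ferritin value for a trend. If the text is followed literally, the discontinued patients disappear from an analysis named ITT. So do the quarterly values they already gave and the central sample drawn when they withdrew.

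At stake is the precision of the slope comparison and, under some dropout patterns, its bias. The mixed model that the plan already intends to fit could use these data directly and would need no imputation.

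**Working it through.** **1. The plan's own figures.** The documents give no figure for the trend test. The surrounding figures reproduce:
- Primary (65% v 67.5%, margin 12.5 points, one-sided 0.025, 80% power): n per arm = (1.96 + 0.84)² × (0.65×0.35 + 0.675×0.325) / (0.125 + 0.025)² = 7.85 × 0.4469 / 0.0225 ≈ 156, so 312 in total against 310 stated.
- Enrolment: 310 / 0.80 = 387.5, so 388 as stated. The allowance is 78 patients (78/388 = 20%).
- Ferritin margin test (155 per arm, SD 1000, margin 400): 400 / (1000 × √(2/155)) = 3.52; Φ(3.52 − 1.96) = 94%, consistent with the stated minimum of 90%.

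**2. Who reaches the trend test.**
- Missed visit, patient continues: value imputed.
- Patient discontinues: no ferritin rule, so the row is incomplete and a classical ANOVA drops it.

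With 20% dropout the analysis rests on about 155 per arm instead of 194.

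**3. Power in closed form.** Assumptions not in the documents: true slope difference 300 ng/mL/year, between-patient slope SD 900, residual SD 350, five quarterly central values (0 to 1 year, sum of squared time deviations 0.625), two-sided 0.05. The SD of a patient's fitted slope is √(900² + 350²/0.625) = 1003, close to the 1000 ng/mL that Section 11.12 gives for ferritin change.
- 194 per arm: SE = 1003 × √(2/194) = 101.8; Φ(300/101.8 − 1.96) = Φ(0.99) = 84%.
- 155 per arm: SE = 1003 × √(2/155) = 113.9; Φ(300/113.9 − 1.96) = Φ(0.67) = 75%.

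**4. Simulation with the protocol's withdrawal rule.** Same SDs plus a random-intercept SD of 1200, withdrawal after a quarterly rise of 1500 ng/mL, and other dropout at random to about 19% in total. Ferritin-driven withdrawal is only about 1%. Completer estimates of a true 300 are 288 to 298 across runs. Completer power is about 73%, against 82% with almost no dropout. The 82% is a benchmark for near-complete follow-up, not the power of the mixed model, which recovers part of the gap.

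**5. When bias becomes material.** Each pattern here is assumed.
- Dropout with probability 0.6 after rises above 450 or 700 ng/mL: completer estimate 262 to 268 for a true 300 (11% to 13% too small), power 62% to 71%. A direct mixed model gives 296 to 298 and 77% to 79%.
- Dropout related to observed ferritin, 23% v 27% by arm, true difference 300: power 71% for completers, 81% for the mixed model and 86% had nobody dropped out. The mixed model regains 10 of the 15 points lost.
- Ferritin-related dropout of 16% v 34%, no true difference: completer bias about 104 ng/mL/year in favour of the arm losing more patients, type I error 16%. The mixed model has bias of about −2 and 4.8%.

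**6. Type I error and imputation.** With 5% missed visits and no dropout, the slope test after imputation rejects 4.8% of the time, so the planned imputation does little harm by itself. If values after dropout were also imputed once and treated as observed, the rate would be 7% to 10%.

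**The case against.** The strongest reply is that the text is underspecified rather than wrong. It does not say that discontinued patients are deleted or that imputation is single. A repeated-measures model can be fitted by likelihood, which keeps partial records. The ITT label and the central sample at withdrawal suggest that those data were meant to count. This is a fair reading, but under it the separate imputation step is unnecessary and the same rewording is needed.

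Three stronger inferences are tempting, and the documents support none of them.
- *The patients lost have the worst trends.* The ferritin rise is one criterion among ten reasons in Section 9, and Section 11.12 does not attribute the 20% to it. At 1500 ng/mL it removes about 1% under the assumed SDs. Bias of 11% to 13% needs triggers of 450 or 700 ng/mL. Unequal dropout is conceivable, since Section 9 and the renal rows of Table 4 contain rules specific to DFX and Section 8 refers to neutropenia induced by DFP. No section supports a split such as 16% v 34%.
- *The false-positive rate is inflated to 7% to 10%.* That requires imputing values after dropout, which Section 11.13 does not plan.
- *Dilution flatters non-inferiority.* The trend test looks for a difference and has no margin. Ferritin non-inferiority is a separate 400 ng/mL comparison of change from baseline.

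**Conclusion.** The point stands as a better choice of method for one supportive secondary analysis. Read with a classical repeated-measures ANOVA, the plan loses the roughly 20% who discontinue from an analysis it calls ITT and wastes ferritin already measured. The expected cost is power: about 73% against 82% with almost no dropout, for an assumed difference of 300 ng/mL/year, assumed variance components and about 19% dropout under the 1500 ng/mL rule. Material bias is conditional on ferritin-related dropout that is much commoner than that rule implies, or that differs between arms. The primary success-rate comparison, the 400 ng/mL non-inferiority test and the figures of 310 and 388 do not change.

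**What to change.** In Section 11.6, replace the repeated-measures ANOVA by a linear mixed model fitted directly to all observed central ferritin values of the ITT set, including the withdrawal values. Include treatment, time, treatment by time and age stratum. Use baseline either as a covariate or as the first response, not both. Entering time as actual elapsed time lets off-schedule withdrawal samples be used. Test the interaction in this model and delete the imputation step from Section 11.13.

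In the same edit, redirect the missing-data cross-reference from Section 11.4 to Section 11.13, and reconcile the monthly ferritin named in Section 11.6 with the quarterly central values designated for formal analyses.

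The cost is SAP wording; no new patients, data or software are needed, because a mixed model is already planned. The drawback is reliance on missing at random: the model in effect carries the observed trend forward after withdrawal. A simple sensitivity analysis, such as shifting the assumed values after withdrawal by a range of amounts in each arm, would show whether the conclusion depends on it.

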12. DATA COLLECTION AND RETENTION

Designated investigator staff must enter the information required by the protocol into the CRF using dedicated computer loaded with fully validated software that conforms the requirements for electronic data capture. Automatic validation programs check for data discrepancies in the electronic CRF and, by generating appropriate error messages, allow modification or verification of the entered data before transfer to Sponsor via a secure internet link. The Principal Investigator must certify that the data are complete and accurate and later receives a CD-ROM or paper copies of the patient data for archiving at the investigational site. All electronic CRFs sent to Sponsor by investigational sites are reviewed upon receipt for any SAEs.

Data on subjects collected on CRFs during the trial will be documented in an anonymous fashion and the subject will only be identified by the patient sequential number. If, as an exception, it is necessary for safety or regulatory reasons to identify the subject, both the Sponsor and the Investigator are bound to keep this information confidential.

The Investigator must maintain source documents for each patient in the study, consisting of all demographic and medical information, including laboratory data, ECGs, etc., and keep a copy of the signed informed consent form. All information on CRFs must be traceable to these source documents in the patient's file.

Essential documents, as listed below, must be retained by the investigator for as long as needed to comply with national and international regulations.

CONFIDENTIAL

DEEP Consortium
DEEP2-Efficacy/Safety Study Protocol

Protocol No. DEEP-2

13. SITE MONITORING

Before study initiation, at a site initiation visit or at an investigator's meeting, a Sponsor or CRO representative will review the protocol and the CRFs with the investigators and their staff. During the study the monitor will visit the site regularly, to check the completeness of patient records, the accuracy of entries on the CRFs, the adherence to the protocol and to GCP, the progress of enrolment, and also to ensure that study medication is being stored, dispensed and accounted for according to specifications. Key trial personnel must be available to assist the field monitor during these visits.

The Investigator must give the monitor access to relevant hospital or clinical records, to confirm their consistency with the CRF entries. No information in these records about the identity of the subjects will leave the study centre. Sponsor monitoring standards require full verification for the presence of informed consent, adherence to the inclusion/exclusion criteria, documentation of SAEs and the recording of primary efficacy and safety variables. Additional checks of the consistency of the source data with the case report forms are performed according to the study-specific monitoring plan.

14. AUDITING PROCEDURES

Audits of clinical research activities in accordance with internal Standard Operating Procedures will be conducted by the Sponsor or CRO to evaluate compliance with the principles of GCP. A regulatory authority may also wish to conduct an inspection (during the study or even after its completion). If an inspection is requested by a regulatory authority, the Principal Investigator must inform the Sponsor immediately that this request has been made.

15. QUALITY ASSURANCE

Data items are entered directly into the study database or indirectly from source data documents by designated and trained investigator staff using single data entry with electronic verification. Sponsor staff reviews the data for completeness and accuracy and instruct the site personnel to make any required corrections or additions. Queries are sent to the investigational site using an electronic data query system which provides an automatic audit trail of the corrections made by designated investigator staff.

Concomitant medications entered into the database will be coded using the World Health Organization (WHO) Drug Reference List which employs the Anatomical Therapeutic Chemical classification system. Coexistent diseases and AEs will be coded using the Medical dictionary for regulatory activities (MedDRA) terminology.

Laboratory samples will be processed centrally and the results will be sent electronically to the Sponsor as specified in the SPM.

When the database has been declared to be complete and accurate, the database will be locked. Any changes to the database after that time can only be made by joint written agreement between the Trial Coordinating Investigator and the Data Manager.

16. ADVERSE EVENTS (AE) AND SERIOUS ADVERSE EVENTS (SAE) REPORTING

According to ICH E6 Guideline (Good Clinical Practice, GCP), both Investigators and Sponsor follow specific procedures when notifying and reporting adverse events/reactions in clinical trials.

The Principal Investigator or qualified site staff is responsible for detecting, documenting and reporting events that meet the definition of an AE or SAE.

AEs will be collected from the start of Investigational Product and until the follow-up contact. Medical occurrences that begin prior to the start of investigational product but after obtaining informed consent should be recorded separately from the Medical History/Current Medical Conditions CRF.

SAEs will be collected over the same time period as stated above for AEs. However, any SAEs assessed as related to study participation (e.g. investigational product, protocol-mandated procedures, invasive tests, or change in existing therapy) will be recorded from the time a subject consents to participate in the study up to 30 days from last dose or study related invasive procedure. All SAEs will be recorded and reported to Safety Contact (SC) within 24 hours after the Investigator has become aware of the event, as indicated in Section 16.3.

16.1 Definitions

In this trial protocol the definitions reported in **Table 8** apply according to the Art.2 of the Directive 2001/20/EC.

Table 8. Definitions

TERM	DEFINITION
‘Adverse Event’ (AE)	any untoward medical occurrence in a patient or clinical trial subject administered a medicinal product and which does not necessarily have a causal relationship with this treatment ^A
‘Adverse Reaction’ (AR)	all untoward and unintended responses to an investigational medicinal product related to any dose administered
‘Serious Adverse Event or Serious Adverse Reaction’ (SAE or SAR)	any untoward medical occurrence or effect that at any dose: 
 ▪ results in death ▪ is life-threatening^B ▪ requires hospitalisation or prolongation of existing hospitalization^C ▪ results in persistent or significant disability or incapacity^D ▪ is a congenital anomaly or birth defect ▪ other medically important/clinically significant events^E
‘Unexpected Adverse Reaction’ (UAR)	an adverse reaction, the nature or severity of which is not consistent with the applicable product information (e.g. Investigator's brochure for an unauthorised investigational product or summary of product characteristics for an authorised product)

^AAn AE can therefore be any unfavourable and unintended sign (including an abnormal laboratory finding), symptom, or disease (new or exacerbated) temporally associated with the use of a medicinal product.

^BThe term 'life-threatening' in the definition of 'serious' refers to an event in which the subject was at risk of death at the time of the event. It does not refer to an event, which hypothetically might have caused death, if it were more severe.

^c In general, hospitalization signifies that the subject has been detained (usually involving at least an overnight stay) at the hospital or emergency ward for observation and/or treatment that would not have been appropriate in the physician's office or outpatient setting. Complications that occur during hospitalization are AEs. If a complication prolongs hospitalization or fulfils any other serious criteria, the event is serious. When in doubt as to whether "hospitalization" occurred or was necessary, the AE should be considered serious.

Hospitalization for elective treatment of a pre-existing condition that did not worsen from baseline is not considered an AE.

^dThe term disability means a substantial disruption of a person's ability to conduct normal life functions. This definition is not intended to include experiences of relatively minor medical significance such as uncomplicated headache, nausea, vomiting, diarrhoea, influenza, and accidental trauma (e.g. sprained ankle) which may interfere or prevent everyday life functions but do not constitute a substantial disruption.

^eMedical or scientific judgment should be exercised in deciding whether reporting is appropriate in other situations, such as important medical events that may not be immediately life-threatening or result in death or hospitalization but may jeopardize the subject or may require medical or surgical intervention to prevent one of the other outcomes listed in the above definition. These should also be considered serious. Examples of such events are intensive treatment in an emergency room or at home for allergic reaction, blood dyscrasias or convulsions that do not result in hospitalization, or development of drug dependency or drug abuse. Events meeting the definition of an AE include:

- Any abnormal laboratory test results (haematology, clinical chemistry, or urinalysis) or other safety assessments (e.g., ECGs, radiological scans, vital signs measurements), including those that worsen from baseline, and felt to be clinically significant in the medical and scientific judgement of the Investigator.
- Exacerbation of a chronic or intermittent pre-existing condition including either an increase in frequency and/or intensity of the condition.
- New conditions detected or diagnosed after investigational product administration even though it may have been present prior to the start of the study.
- Signs, symptoms, or the clinical sequelae of a suspected interaction.
- Signs, symptoms, or the clinical sequelae of a suspected overdose of either investigational product or a concomitant medication (overdose per se will not be reported as an AE/SAE).

Events that do not meet the definition of an AE include:

- Any clinically significant abnormal laboratory findings or other abnormal safety assessments that is associated with the underlying disease, unless judged by the Investigator to be more severe than expected for the subject's condition.
- The disease/disorder being studied or expected progression, signs, or symptoms of the disease/disorder being studied, unless more severe than expected for the subject's condition.
- Medical or surgical procedure (e.g., endoscopy, appendectomy); the condition that leads to the procedure is an AE.
- Situations where an untoward medical occurrence did not occur (social and/or convenience admission to a hospital).
- Anticipated day-to-day fluctuations of pre-existing disease(s) or condition(s) present or detected at the start of the study that do not worsen.

